11 COLLABORATIVE AGREEMENTS

11.1 AGREEMENT TYPE

Springworks is providing the agent used in this study to the PI under a Collaborative Agreement (CTA); providing this agent constitutes the research support for this investigator-initiated study.

Version Date: 5-18-2023

12 HUMAN SUBJECTS PROTECTIONS

12.1 RATIONALE FOR SUBJECT SELECTION

Men and women of all races and ethnic groups are eligible for this trial.

12.2 PARTICIPATION OF CHILDREN

Because no dosing or adverse event data are currently available on the use of Nirogacestat in patients <18 years of age, children are excluded from this study, but may be eligible for future pediatric trials.

12.3 EVALUATION OF BENEFITS AND RISKS/DISCOMFORTS

This study will be open to all individuals regardless of gender, ethnicity, or race, provided that the aforementioned inclusion and exclusion criteria are met. Patients for this study will be recruited through internal referral, our physician referral base, and through various cancer information hotlines (i.e., Clinical Studies Support Center, [name]). To date, there is no information that suggests that differences in drug metabolism or effect on tumor would be expected in one ethnic group compared to another. Efforts will be made to extend accrual to each representative population, but a balance must be struck between participant safety considerations and limitations on the number of individuals exposed to potentially ineffective treatments on the one hand and the need to explore racial/ethnic aspects of clinical research on the other hand. If differences in outcome that correlate to ethnic identity are noted, a follow-up study may be written to investigate those differences more fully.

12.3.1 Patient Advocate

The patients' rights representative is available to patients receiving treatment on this protocol at the NIH Clinical Center at [contact] in [name], on the Bethesda NIH campus. Patients will be informed that they can contact the study PI or RN at any time with questions about their medical care, and that the patients' rights representative is also available to answer non-medical questions about the study.

12.4 RISKS/BENEFITS ANALYSIS

There may or may not be any clinical benefit to a patient from participation in this trial. Their participation will benefit future cancer patients. Potential risks include the possible occurrence of any of a range of nirogacestat side effects (listed in Section 13.1.1), gene sequencing risks (Section 5.4.2), MRI imaging risks (Section 13.2), and phlebotomy and CT radiation and contrast agent risks (details below). The procedure for protecting against or minimizing risks will be to medically evaluate patients as described in Section 3. Although no compensation is available, any injury will be fully evaluated and treated in keeping with the benefits or care to which participants are entitled under applicable regulations.

All care will be taken to minimize side effects, but they can be unpredictable in nature and severity. This study may involve risks to patients, which are currently unforeseeable. All patients will be monitored for side effects from taking study medication. This research

represents a greater than minimal risk to participants, but presents the prospect of direct benefit to individual subjects.

Risks Related to CT Radiation: This study includes 2 optional CT-guided tumor biopsies and up to 3 CT restaging scans per year. These procedures confer radiation exposure at an effective dose of up to approximately 6 rem per year. This dose is above NIH RSC guidelines of less than 5.0 rem per year in adults.

Risks Related to Contrast Agents:

Risks for IV Contrast: Symptoms from the contrast infusion are usually mild and may include discomfort from the injection, feeling hot, a metallic taste, nausea or vomiting, and allergic reaction (ranging from mild itching or rash to severe trouble breathing, shock or, rarely, death). The contrast may also cause kidney problems.

Risks for Oral Contrast: Symptoms from oral contrast are usually mild and may include vomiting, nausea, cramping, bloating, constipation, or diarrhea.

Risks Related to Phlebotomy: There are no major risks involved with blood draws. Minor complications include bleeding, pain, bruising at the site of phlebotomy, vasovagal reactions or infections may rarely occur.

12.5 CONSENT AND ASSENT PROCESS AND DOCUMENTATION

An associate or principal investigator on the trial will inform patients of the purpose, alternatives, drug administration plan, research objectives, and follow-up of this trial. The patient will be provided an IRB-approved consent for review and signature and his/her questions will be answered. After a decision is made to enroll into the study, a signature will be obtained from the patient. The original signed consent goes to Medical Records; a copy will be placed in the research record. Patients will not be consented by telephone

All patients must have a signed informed consent form and an on-study (confirmation of eligibility) form filled out and signed by a participating investigator before entering on study.

When a hand signature on an electronic document is used for the documentation of consent, this study will use the iMedConsent platform (which is 21 CFR Part 11 compliant) to obtain the required signatures. Both the investigator and the participant will sign the electronic document using a finger, stylus, or mouse. Electronic signatures (i.e., "signatures" that are digitally generated) will not be used.

12.5.1 Participation of subjects unable to give consent

Adults unable to give consent are excluded from enrolling in the protocol. However, re-consent may be necessary and there is a possibility, though unlikely, that subjects could become decisionally impaired. For this reason and because there is a prospect of direct benefit from research participation (*i.e.*, long-term stabilization and/or improvement in the pain and physical impairment caused by desmoid tumors), all subjects \geq age 18 at the NCI only will be offered the

Version Date: 5-18-2023

opportunity to fill in their wishes for research and care, and assign a substitute decision maker on the "NIH Advance Directive for Health Care and Medical Research Participation" form so that another person can make decisions about their medical care in the event that they become incapacitated or cognitively impaired during the course of the study. Note: The PI or AI will contact the NIH Ability to Consent Assessment Team (ACAT) for evaluation as needed for the following: an independent assessment of whether an individual has the capacity to provide consent; assistance in identifying and assessing an appropriate surrogate when indicated; and/or an assessment of the capacity to appoint a surrogate. For those subjects that become incapacitated and do not have pre-determined substitute decision maker, the procedures described in MAS Policy 19-1 and NIH OHSRP Policy 403 for appointing a surrogate decision maker for adult subjects who are (a) decisionally impaired, and (b) who do not have a legal guardian or durable power of attorney, will be followed.

13 PHARMACEUTICAL AND DEVICE INFORMATION

13.1 NIROGACESTAT (PF-03084014) (IND #119,769)

PF-03084014 is an investigational agent supplied by SpringWorks; the dihydrobromide salt form will be used in the clinical studies.

Molecular Weight: 651.47 (dihydrobromide salt)

Molecular Formula: C₂₇H₄₃Br₂F₂N₅O

Physical Description: white to off-white powder

Route: oral

Mechanism of Action: selective noncompetitive inhibitor of γ -secretase

Contraindications: none identified

Other Names: PF-4014

13.1.1 Nirogacestat Toxicity

Preclinical—The target systems reported in chronic oral dosing studies in dogs were the GI, hematopoietic/immune, musculoskeletal, reproductive, and hepatic systems. Hematopoietic/immune effects were seen in both rat and dog, and included decreases in B and T cells, NK cells, IgM and IgD expression on B cells (rat only), and lymphoid depletion in spleen, thymus (thymic cortical atrophy in dog), lymph nodes, and/or gut-associated lymphoid tissue. Treatment-related intestinal tract changes consisted of epithelial hyperplasia and, with higher exposures, epithelial degeneration and necrosis (more detailed information is provided in Section 1.2.2).

Clinical—The most common AEs independent of causality seen in patients with advanced solid tumors were diarrhea, nausea, fatigue, vomiting, hypophosphatemia, decreased appetite, cough and rash; all of these events were considered to be treatment related in some patients. The majority of AEs were considered mild to moderate but treatment related Grade 3 hypophosphatemia, diarrhea, and rash have been frequently reported. The only treatment-related

Grade 4 AE was anaphylactic shock reported in one patient, an event thought to be related to co-administration of intravenous morphine.

No clinically relevant changes in vital signs or electrocardiograph endpoints have been reported. The severe hematology laboratory test abnormalities reported were low lymphocyte count and platelets. The most frequently reported severe serum chemistry abnormalities were hypophosphatemia, hypokalemia and hyperglycemia (more detailed information is provided in Section 1.2.2).

As of April 25, 2023, Springworks identified non-melanoma skin cancer (defined as the MedDRA Preferred terms of Basal cell carcinoma, Squamous cell carcinoma, and Squamous cell carcinoma of the skin) as an important potential risk for nirogacestat, based on occurrence in six nirogacestat trial participants. All participants have continued treatment with nirogacestat after

the report of their non-melanoma skin cancer [with three patients on extended treatment, up to 1448 days after onset of their non-melanoma skin cancer] with no reported occurrence of another non-melanoma skin cancer. No reports of malignant melanoma have been reported from participants in the nirogacestat development program. SpringWorks recommended that an association between treatment with nirogacestat and the appearance and diagnosis of non-melanoma skin cancer be recognized as an important potential risk for nirogacestat, and this risk has been added to the informed consent form with Amendment R (version date 5/18/2023).

13.1.2 Formulation and Preparation

Nirogacestat is available as 10 mg and 50 mg tablets. All tablets contain common compendial excipients.

13.1.3 Stability and Storage

Tablets should be stored at 15-25° C (59-77°F).

13.1.4 Incompatibilities/Drug Interactions

In vitro studies indicate that Nirogacestat is metabolized primarily by the drug-metabolizing enzyme, CYP3A4. Nirogacestat does not inhibit CYP1A2, weakly inhibits CYP2C9, CYP2C19 and CYP2D6, and causes induction of CYP3A4. Nirogacestat may however increase exposure to sensitive substrates of CYP2C9, CYP2C19, and CYP2D6, or CYP2C9, CYP2C19, and CYP2D6 substrates with a narrow therapeutic range.

- Cytochrome P450 Inhibitors: Co-administration of Nirogacestat with potent inhibitors of CYP3A4 may increase plasma Nirogacestat concentrations. Caution should be exercised in patients receiving Nirogacestat in combination with these and other potent CYP3A4 inhibitors (see Appendix C).
- Cytochrome P450 Inducers: Nirogacestat metabolism may be induced when taking potent CYP3A4 inducers resulting in reduced Nirogacestat plasma concentrations. Caution should be exercised in patients receiving Nirogacestat in combination with these and other potent CYP3A4 inducers (see Appendix C).
- Cytochrome P450 Substrates: Patients treated with Nirogacestat should avoid the use of CYP3A4 substrates with narrow therapeutic indices (see Appendix C).

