PF-03084014 induced CYP 3A4 in human hepatocytes in vitro. Nirogacestat does not inhibit CYP 1A2 at concentrations <30 μM, but weakly inhibits CYP 2C9, CYP 2C19 and CYP 2D6 in human liver microsomes with 50% inhibitory concentration (IC₅₀) values of 18.5 +/- 1.6 μM, 20.3 +/- 2.0 μM and 13.5 +/- 1.2 μM. PF-03084014 inhibits CYP 3A with an IC₅₀ value of 4.6 +/- 0.3 μM. Additionally, preliminary assessment suggests that Nirogacestat is a weak time-dependent inhibitor of CYP 3A4 with an inhibition constant (Ki) value of 2.2 μM and a kinact rate of 0.059/min. In a healthy volunteer clinical drug-drug interaction study, Nirogacestat increased the area under the plasma concentration-time curve from zero to infinity (AUC_{0-∞}) 58.9% and maximum observed plasma concentration (C_{max}) 30.7% of Midazolam following 9 days of dosing at 95 mg daily. In nonclinical studies conducted in *mdr1a/1b* (-/-) knockout and wild-type mice, PF-03084014 readily penetrates the blood-brain barrier and shows interaction with the efflux transporter P-glycoprotein (P-gp) at the blood-brain barrier.

Correlative Studies Background

Pre- and post-dose (cycle 1) blood and hair follicle samples were collected for pharmacodynamic analysis on the Phase I clinical trial in patients with advanced solid tumors. Changes in gene expression in these samples were measured by TaqManR qRT-PCR. Notch pathway modulation was demonstrated in all evaluable patients, with transcriptional repressor *Hes4* showing the most consistent regulation, with a greater than 2-fold down-regulation in an initial cohort of nine patients (Figure 4) [20]. *Hes4* is also one of several Notch pathway target genes down-regulated following Nirogacestat treatment in breast cancer xenograft models [25] (Figure 2).

[figure not shown]

Figure 4: Changes in *Hes4* gene expression following treatment with Nirogacestat in samples from 9 patients on the Phase I trial [20].

In this current study, optional tumor biopsies will be collected at baseline and during cycle 7 to look at changes in the expression of Notch response genes in the Clinical Tumor Profiling Laboratory of [name], CCR. A blood sample will also be collected at baseline; blood and tumor biopsy samples will undergo genotyping for germline and somatic mutations in *APC* and *CTNNB1* genes.

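### Section 13.1.4 describes nirogacestat's effect on CYP3A4 as induction only and leaves CYP3A4 out of its raised-exposure warning, although Section 1.2.2 reports CYP3A inhibition in vitro and a 58.9% rise in midazolam AUC in humans

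*Combined protocol and SAP*

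**What the plan says.** Section 13.1.4 first identifies CYP3A4 as the main enzyme that metabolises nirogacestat. It then gives the drug's own effect on each enzyme: "Nirogacestat does not inhibit CYP1A2, weakly inhibits CYP2C9, CYP2C19 and CYP2D6, and causes induction of CYP3A4". The exposure warning follows directly: "Nirogacestat may however increase exposure to sensitive substrates of CYP2C9, CYP2C19, and CYP2D6". That sentence goes on to cover narrow-range substrates of the same three enzymes. CYP3A4 substrates appear only in a later bullet: "Patients treated with Nirogacestat should avoid the use of CYP3A4 substrates with narrow therapeutic indices". The introduction to Appendix C repeats this avoidance rule. Neither place says whether exposure to a CYP3A4 substrate would rise or fall.

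Section 1.2.2, under its heading on potential drug interactions, gives a fuller account. Induction is reported with its setting: "PF-03084014 induced CYP 3A4 in human hepatocytes in vitro". The same paragraph then reports direct inhibition ("PF-03084014 inhibits CYP 3A with an" IC50 of 4.6 ± 0.3 µM). As a preliminary assessment it adds that "Nirogacestat is a weak time-dependent inhibitor of CYP 3A4 with an inhibition constant" of 2.2 µM (kinact 0.059/min). Finally, it describes a healthy-volunteer interaction study in which AUC rose "58.9% and maximum observed plasma concentration" rose "30.7% of Midazolam following 9 days of dosing at 95 mg daily". Appendix C lists midazolam among the CYP3A4 substrates.

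**The concern.** Section 13.1.4 is the section a prescriber or pharmacist would consult about a co-medication. It sorts the enzymes into not inhibited, weakly inhibited and induced, and puts CYP3A4 in the last group alone. The natural reading is that CYP3A4 substrates can only lose exposure. The raised-exposure sentence reinforces this by naming the three weakly inhibited enzymes and omitting CYP3A4.

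The human evidence elsewhere in the protocol points the other way. What is at stake is safety guidance. A patient taking a sensitive CYP3A4 substrate without a narrow therapeutic index could have raised exposure, and the interaction section would lead the clinician to look for the opposite. Such co-medication is foreseeable: Section 4 allows aprepitant and 5-HT3 antagonists for nausea, and Appendix C lists aprepitant and ondansetron as CYP3A4 substrates. The documents do not say whether either counts as sensitive, so this shows relevance, not harm.

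**Working it through.** No sample-size or error-rate figure is involved. The check is a comparison of two sections, with simple ratios for scale.

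**Step 1: what each section says about CYP3A4**

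| Point | Section 1.2.2 | Section 13.1.4 |
|---|---|---|
| Induction | Yes, in human hepatocytes in vitro | Yes, setting not stated |
| Direct inhibition | Yes, IC50 4.6 ± 0.3 µM | Not mentioned |
| Time-dependent inhibition | Weak and preliminary, Ki 2.2 µM | Not mentioned |
| Human midazolam study | AUC +58.9%, Cmax +30.7% | Not mentioned |
| Raised exposure of CYP3A4 substrates | Shown for midazolam | Absent from the warning |

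Section 13.1.4 carries over one of the four findings. It has no pointer back to Section 1.2.2, although Section 13.1.1 does refer the reader there.

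**Step 2: direction and size of the human result**

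- AUC ratio = 1 + 0.589 = 1.59
- Cmax ratio = 1 + 0.307 = 1.31

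Midazolam was measured after 9 days of nirogacestat, so the result reflects the balance of whatever induction and inhibition were present at 95 mg daily. That balance was a rise in exposure.

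**Step 3: in-vitro potency against the enzymes that are in the warning**

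The IC50 values in Section 1.2.2 are 13.5 ± 1.2 µM (CYP2D6), 18.5 ± 1.6 µM (CYP2C9), 20.3 ± 2.0 µM (CYP2C19) and 4.6 ± 0.3 µM (CYP3A).

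- CYP2D6 / CYP3A = 13.5 / 4.6 = 2.9
- CYP2C9 / CYP3A = 18.5 / 4.6 = 4.0
- CYP2C19 / CYP3A = 20.3 / 4.6 = 4.4

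Taking the ± limits at their extremes, the smallest ratio is (13.5 − 1.2) / (4.6 + 0.3) = 12.3 / 4.9 = 2.51. The largest is (20.3 + 2.0) / (4.6 − 0.3) = 22.3 / 4.3 = 5.19. CYP3A has the lowest IC50 throughout. The enzyme left out of the warning is thus the one most potently inhibited in vitro, and the only one with a human result.

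**Step 4: what cannot be computed**

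The IC50 ratios rank in-vitro potency and nothing more. Section 1.2.2 gives a human unbound fraction of 2.61%, but the documents give no human plasma concentration at 150 mg BID to set against the IC50 values. The trial's daily dose is 2 × 150 = 300 mg, and 300 / 95 = 3.2 times that of the midazolam study. This is a dose ratio, not an exposure ratio, and should not be used to scale the 58.9%. The size and direction of the net CYP3A4 effect at the trial dose are therefore unknown.

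**The case against.** The best defence is that no clause in Section 13.1.4 is false. Section 1.2.2 does report CYP3A4 induction, the raised-exposure sentence is correct for the enzymes it names, and it does not claim to be exhaustive. CYP3A4 substrates also have their own bullet with a firmer instruction than the other enzymes receive: narrow-index CYP3A4 substrates are to be avoided, and that rule protects whichever way exposure moves. The missing data are in the same document under a heading on the same subject. Further safeguards exist. The investigator reviews concurrent medications at entry (2.1.2.1), they are reviewed periodically on study (Section 4), and HIV-positive patients on combination antiretroviral therapy are excluded because of possible pharmacokinetic interactions (2.1.2.7). Section 13.1.4 also opens by referring to in-vitro studies.

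Much of this stands, and it limits the practical risk. The induction clause is incomplete, not untrue. But the gap is not closed:

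- The avoidance rule covers narrow-index substrates only. For the other three enzymes, 13.1.4 treats sensitive substrates as a separate group, so on its own scheme sensitive CYP3A4 substrates are unaddressed.
- A medication review depends on its reference text, and this text suggests the wrong direction.
- The antiretroviral exclusion does not bear on other sensitive CYP3A4 substrates.
- The opening reference to in-vitro studies governs the sentence about how nirogacestat is metabolised, not the sentence about induction.

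**Conclusion.** The concern holds. As a summary of nirogacestat's effect on CYP3A4, Section 13.1.4 is misleading: it keeps the in-vitro induction finding without that label and drops the contrary evidence, including the protocol's only human interaction result (midazolam AUC 1.59-fold, Cmax 1.31-fold at 95 mg daily). Its raised-exposure warning omits the enzyme that result concerns.

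This conclusion rests on the text of the two sections and on Appendix C classing midazolam as a CYP3A4 substrate. It does not assume that inhibition predominates at 150 mg BID, which the documents leave open. Because existing safeguards cover part of the risk, this is a correction that should be made, not evidence that patients were harmed. The primary response-rate analysis and its decision rule are unaffected.

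**What to change.** Amend Section 13.1.4 as follows:

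1. Label CYP3A4 induction as an in-vitro finding.
2. State that CYP3A4 inhibition was also seen in vitro and that midazolam exposure rose in healthy volunteers at 95 mg daily, with a cross-reference to Section 1.2.2 of the kind Section 13.1.1 already uses.
3. Add CYP3A4 to the sentence on increased exposure of sensitive substrates.
4. State that the net effect on CYP3A4 at 150 mg BID is unknown.
5. Keep the rule on narrow-therapeutic-index CYP3A4 substrates unchanged.

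The cost is two or three sentences at the next amendment. No new data, procedures, monitoring or visits are needed.

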13.2 MAGNETIC RESONANCE IMAGING SCANNER

The use of Magnetic Resonance Imaging scanners on this study for assessment of disease burden meets the requirements for an IDE exemption under Category 1. The devices in the Clinical Center are commercially obtained and FDA approved. The device is being used in accordance with FDA labeling and was not regulated as a device before the enactment of the Medical Device Amendments

13.2.1 Source

MRI scans will be performed using the devices available in the NIH Clinical Center.

13.2.2 MRI and Contrast Agent Toxicity

Risks associated with MRIs include the following: participants may be at risk for injury from the MRI magnet if they have some kinds of metal in their body. It may be unsafe for participants to have an MRI scan if they have a pacemaker or other implanted electrical device, brain stimulator; some types of dental implants, aneurysm clips, and metallic prostheses (including metal pins and rods, heart valves, and cochlear implants); permanent eyeliner; implanted delivery pump; or shrapnel fragments. Welders and metal workers may have small metal fragments in the eye. Participants will be screened for such metal before having any scan. If they have any, you will not receive an MRI scan. If they have a question about metal in their body, they should inform the study investigators. Participants will be asked to complete an MRI screening form before each MRI scan they have.

All magnetic objects must be removed before entering the MRI scan room. This includes items like watches, coins, jewelry, and credit cards.

People with fear of confined spaces may become anxious during an MRI. Those with back problems may have back pain or discomfort from lying in the scanner. The noise from the scanner is loud enough to damage hearing, especially in people who already have hearing loss. Everyone having a research MRI scan will be fitted with hearing protection. If the hearing protection comes loose during the scan, participants should let us know right away.

Symptoms from the contrast infusion are usually mild and may include feeling hot, burning, or coldness in the arm during the injection, a metallic taste, headache, allergic reactions and nausea. In an extremely small number of individuals, more severe symptoms have been reported including shortness of breath, wheezing, hives, and lowering of blood pressure. Unless specifically allowed by the protocol, participants will not receive gadolinium-based contrast agents for research purposes if they have previously had an allergic reaction to them. Individuals with a history of anaphylaxis to other agents or chronic asthma requiring treatment will not receive gadolinium under this protocol unless they have previously received gadolinium and tolerated it well. Participants will be asked about such allergic reactions and history of asthma before a contrast agent is administered.

People with kidney disease are at risk for a serious reaction to gadolinium contrast called "nephrogenic systemic fibrosis," which has resulted in a very small number of deaths. If subjects are 60 years old or greater or have diabetes, kidney disease or liver disease, blood work to assess kidney function will be performed within 4 weeks before any MRI scan with gadolinium contrast. Participants may not receive gadolinium for a research MRI scan if kidney function is not normal. There is no evidence for the potential of gadolinium-related toxicity in people with normal kidney function. This protocol follows NIH Clinical Center guidelines for kidney-function screening related to gadolinium administration.

Most of the gadolinium contrast is eliminated in the urine. However, recent studies have found very small amounts of residual gadolinium in the body, including the brain, by imaging and at autopsy. Macrocyclic gadolinium-containing contrast agents are substantially less likely to leave gadolinium behind than linear agents. The use of macrocyclic vs. linear agents in this study is delineated in the procedures section above. There is presently no evidence that the retained gadolinium is associated with any adverse effects.

REFERENCES

- 1. de Bree, E., et al., *Desmoid tumors: need for an individualized approach*. Expert Review of Anticancer Therapy, 2009. **9**(4): p. 525-535.
- 2. Lev, D., et al., *Optimizing Treatment of Desmoid Tumors*. Journal of Clinical Oncology, 2007. **25**(13): p. 1785-1791.
- 3. Lewis, J., et al., *The Enigma of Desmoid Tumors*. Annals of Surgery, 1999. **229**(6): p. 866-872.
- 4. Alman, B., et al., *Increased beta-catenin protein and somatic APC mutations in sporadic aggressive fibromatoses (desmoid tumors)*. Am J Pathol, 1997. **151**(2): p. 329-34.
- 5. Lips, D.J., et al., *The role of APC and beta-catenin in the aetiology of aggressive fibromatosis (desmoid tumors)*. European Journal of Surgical Oncology (EJSO), 2009. **35**(1): p. 3-10.
- 6. Miyoshi, Y., et al., Frequent mutations in the β -catenin gene in desmoid tumors from patients without familial adenomatous polyposis. Oncology Research, 1998. **10**(11-12): p. 591-594.
- 7. Huss, S., et al., β -Catenin (CTNNB1) mutations and clinicopathological features of mesenteric desmoid-type fibromatosis. Histopathology, 2013. **62**(2): p. 294-304.
